## 1. AMENDMENT HISTORY

Amendment No.	Protocol Version No.	Date issued	Author(s) of changes	Details of Changes made

## 2. SYNOPSIS

It may be useful to include a synopsis of the study for quick reference. Delete or alter as appropriate/required.

Study Title	The BCAE Study: Best Care for Abdominal Emergencies
Internal ref. no.	PHT/2019/72
Problem statement	Abdominal emergencies are common, involving perforation, obstruction or ischaemia of the bowel, often needing life-saving emergency surgery, with a large incision to access the abdominal cavity called "laparotomy". This procedure is high risk with 10% mortality rate. 30,000 emergency laparotomies are performed each year in England and Wales. Since 2013, the National Emergency Laparotomy Audit (NELA) has set standards of care and monitored outcomes for emergency laparotomy, which has reduced mortality from 11.8 to 9.5%. However, patients who do NOT have a laparotomy are not well characterised and do not receive the prioritised care patients having surgery do, even though their condition is no less severe. Initial research has shown a surprisingly large group of patients (32%) with an intestinal emergency do not have surgery and have 30-day mortality of 63%. There are two additional groups of patients admitted with abdominal emergencies: patients having keyhole surgery and patients for whom any treatment would be futile and would benefit most from an end of life care pathway. Clearly further work is needed to investigate the management of ALL patients with intestinal emergency, to optimise care for each group of patients.
Research question / hypothesis	The aim of this study is to improve care for all patients with an intestinal emergency, irrespective of whether they have surgery or not.
Study Design	This is a single-centre retrospective cohort study utilising electronic hospital records.
Study Participants	
Data will be derived from electronic patient records collected as part of routine clinical patient care on all general adult wards (excluding maternity) between 2013 and 2020.
 
Inclusion criteria:
 
 
• Must have an acute intestinal condition, based on their ICD-10 codes and OPSC-4 codes
 
• Must be <math>\geq 16</math> years of age at the time of admission
 
• Have at least one full set of vital signs recorded on the day of admission
 
• Have at least one full set of routine blood tests recorded on the day of admission
 
 
Exclusion criteria:
 
 
• Maternity admissions during/after pregnancy
 
• Patients admitted or undergoing abdominal surgery for a second time or more
 
 
Using OPCS-4 codes from PAS and TheatreMan™ and NELA data, we will then identify patients who had an emergency laparotomy, and those who had a laparoscopic procedure. We aim to identify a further group where treatment is futile, suggesting that an early focus on end of life care might be appropriate.

Planned Sample Size	2,500
Follow-up duration	1 year (retrospectively)

Planned Study Period	01 Dec 2020 – 31 May 2021
Primary Objective	Provide mortality rates for different treatment options, and analysis of short- and long-term outcomes.
Secondary Objectives	Define patient sub-groups with similar health characteristics based on clinical data and an established risk index.  Use statistical analysis to predict the risk of death for each patient group and treatment option, which will allow us to identify the best care pathways for each cluster.
Primary Endpoint	Mortality risk for each treatment group
Secondary Endpoints	Risk of other outcomes and long-term complications and association between patient factors and these outcomes
Intervention (s)	N/A

### 3. ABBREVIATIONS

AUROC	Area Under the receiver operating characteristic curve
EWS	Early warning score
ICD-10	International Classification of Diseases, version 10
GDPR	General Data Protection Regulation
LDTEWS	Laboratory decision tree early warning score
NELA	National Emergency laparotomy audit
NEWS	National early warning score
NHS	National Health Service
OPCS-4	Office of Population Censuses and Surveys, Classification of Surgical Operations and Procedures (4th revision)
PAS	Patient Access system
PHUT	Portsmouth Hospitals University Trust
P-POSSUM	Portsmouth Physiological and Operative Severity Score for the enUmeration of Mortality and morbidity
PRA	Patient Research Ambassador
QI	Quality improvement
UoP	University of Portsmouth
IEWS	VitalPac Early warning score

## 4. BACKGROUND AND RATIONALE

### 4.1 What is the problem being addressed?

30,000 emergency abdominal laparotomies are performed each year in England and Wales (1). Each involves making a large incision down the middle of the abdomen to gain access to the abdominal cavity. In 2011, the Royal College of Surgeons England issued a report highlighting concerns that the mortality rate for patients having laparotomy was about twice that of open-heart surgery, with a number of shortfalls in patient care contributing to this (2, 3). Since 2013, the National Emergency Laparotomy Audit (NELA) has monitored outcomes from emergency laparotomy across the UK. The audit sets standards of care against which hospitals are benchmarked, such as early administration of antibiotics, CT-scan for diagnosis, pre-operative risk assessment, consultant surgeon/anaesthetist presence in theatre and transfer to intensive care postoperatively, leading to better outcomes (1, 4-6).

Conversely, patients with intestinal emergencies who do NOT have a laparotomy are not well characterised and do not receive the prioritised care that patients having surgery do; even though their condition is no less severe. There is a significant lack of information on the outcome and quality of life of patients who do not have a laparotomy. In the UK, only a single small study, the NoLap Study (7), has looked at this. They found a 30-day mortality of 63% in these patients compared to 13% for those who had a laparotomy. It is this surprisingly large group of patients (32%), who have such a poor outcome that deserves further investigation.

This study will benefit patients by providing information on the outcomes for ALL patients admitted with an intestinal emergency. Effective alternatives to laparotomy exist, including keyhole (laparoscopic) surgery (8-12) and interventional radiology procedures (13-16). These are less invasive and could carry lower risks than a laparotomy. By identifying groups of patients for whom these less invasive procedures may be more appropriate, the development of new alternative care pathways for them can be prioritised. There will sadly be some patients for whom active treatment is futile, such as those with loss of blood supply to the bowel or advanced cancer (17). Defining this patient group too will facilitate the development of pathways that have an earlier focus on symptomatic best end of life care. The characteristics of patients and their outcomes undergoing all the above 4 options will be investigated. Knowing these risks will help us better inform patients of the likely outcomes of their choices.

### 4.2 Why is this important?

Patients who do have a laparotomy are high risk, with a 10% mortality rate at 30 days measured nationally. This group is closely scrutinised by the National Emergency Laparotomy Audit (NELA) who set strict standards of care, and outcomes from surgery are well characterised (1, 2, 4-6). However, there is clear evidence that patients with intestinal emergencies who do NOT have emergency abdominal surgery (laparotomy) do very poorly, with only 30% of patients surviving to a year from admission (7). Our concern is that patients not undergoing laparotomy, but with the same life-threatening pathology, are being forgotten and do not receive the focus of care that they deserve. To improve the quality of care for these patients, better understand the risk of mortality and associated patient factors for ALL patients admitted with an intestinal emergency is needed.

This much-needed study will benefit patients by providing information on the 30-day and 1-year mortality for all patients with an intestinal emergency admitted to our hospital over a 6.5-year period. By observing relationships between mortality and patient factors like age, diagnosis, co-morbidities, vital signs, blood tests and surgery versus no-surgery, factors influencing patient outcomes will be identified and better understood. The "NoLap" study (7) suggested that a cohort of these patients who didn't have a laparotomy might in retrospect have had a better chance of survival if they had. To investigate this, patient factors will be analysed and patterns that significantly influence mortality will be determined. Results will provide insights into the different patient groups and improve our

understanding of their risk of death, with or without surgery. This will enable clinicians to more intelligently advise patients and their relatives on risks of laparotomy against alternative management.

The NoLap study does not provide information on the performance of laparoscopic (keyhole) procedures compared to laparotomies for abdominal emergencies. PHUT has championed the use of laparoscopy in emergency surgery, with progressive uptake by all consultants from 2014 onwards (11). By 2018, 60% of cases were completed laparoscopically, far higher than the national average of 8% (1). More importantly, this approach has been shown to be safe, with reduced mortality and length of stay (11). For patients unfit or unable to have any surgery, the Department of Interventional Radiology provides an on-call service to drain sepsis and embolise bleeds under local anaesthesia. In this study, information on the outcomes for patients who had an intestinal emergency managed laparoscopically or had an interventional radiology procedure will be collected. The effect of alternative treatments on patient outcomes will be assessed to determine which patient groups would most likely benefit from these interventions. This will benefit patients by providing clinicians with the scientific knowledge needed to develop better care pathways using these less invasive procedures. This will provide clinicians and their patients with the evidence they need to make a better-informed choice between laparotomy, minimally invasive procedures and symptomatic end of life care.

#### **4.3 Why is this research needed now (existing evidence)?**

Emergency laparotomy remains a common, high-risk operation (1). It is mostly performed for emergencies where there is perforation, obstruction or ischaemia of the bowel (intestine) that could lead to peritonitis. These are time critical pathologies requiring urgent treatment and careful peri-operative care, with a poor chance of survival without surgery (2-3). Since 2013, the National Emergency Laparotomy Audit (NELA) has monitored outcomes from emergency laparotomy across the UK, with a strong focus on identifying high-risk patients, ensuring consultant-led care and admission to intensive care postoperatively to improve outcomes (1, 4-6).

However, very little research has investigated the outcomes and the care received by patients with intestinal emergencies who do not have a laparotomy. The NoLap study (7) collected data on 314 patients admitted with an intestinal emergency and found a substantial patient group (32%) who do not have surgery. Of these, 74% were not felt to be fit enough for laparotomy, 6% had advanced cancer, 4% declined surgery and 16% undocumented. The 30-day mortality rate for patients with laparotomy was 13%, in-line with expected outcomes, yet the rate for patients who did not have surgery was 63%. This group were older (78 vs 63.7 years old) and frailer (30% vs 81%) and more likely to have co-morbidities. This study will build on this information to provide clear answers about which patient groups could benefit from laparotomy or alternative, less-invasive treatments. Factors significantly influencing mortality will be identified for clinicians to better inform patients/relatives of risks of their treatment. The NoLap study also compared two surgical risk models (18-19) to benchmark outcomes (7). Observed mortality (13%) in the laparotomy group closely matched the predicted mortalities (12% and 17%).

However, predicted mortality for the patients who did not have surgery was much lower (30% and 40%) than the actual observed mortality (63%). This suggests that some patients who were perceived as not fit enough for surgery actually had a better chance of survival with a laparotomy. This highlights the need to better understand why patients with intestinal emergencies do/do not have a laparotomy: why are patients not receiving the best possible care and so missing potentially life-saving treatment? The discrepancy could be due to unmeasured confounding patient factors that are not included in the risk model. Our study will identify the factors that influence mortality, enabling clinicians to select the best care pathway for individual patients and benefit those who may have been advised against surgery in the past, but for whom surgery (possibly using a laparoscopic approach) may indeed be the best way forward.

NELA standards of care have reduced 30-day mortality in emergency laparotomy from 11.8% to 9.5% since 2013(1, 4-6). However, the NoLap study (7) indicated these standards of care were less

frequently achieved in patients who did not have surgery. Decisions not to operate were less often informed by a CT scan (67% vs 82%), risk assessed (24% vs 37%), or involved documented consultant decision (66% vs 83%). There are possibly other factors that have influenced the decision not to operate, such as severe health problems precluding anaesthetic. Nevertheless, this highlights concerns that patients not having laparotomy are less likely to receive the same high standards of care. This study therefore seeks to redress this by focusing on *all* patients with abdominal emergencies, not just those who have had a laparotomy, to also improve the outcome of this neglected group of patients.

#### 4.4 Impact of research

This study will provide new information on the outcomes for ALL patients with abdominal emergencies and the treatment they receive. By identifying groups of patients for whom less invasive procedures or end of life care may be more appropriate, it will support the development of new alternative care pathways.

This study will contribute novel information on the outcomes of minimally invasive procedures in abdominal emergencies (laparoscopy and interventional radiology). This information will be highly relevant to acute hospitals providing an emergency general surgery service across the UK. Initial analysis of the national NELA database has shown that currently only 8% of surgeries for abdominal emergencies in the UK are performed laparoscopically. Early data from Portsmouth Hospitals NHS Trust suggests patients may do better with this approach. The findings from this study will provide the necessary evidence to increase the proportion of laparoscopies nationwide and, thus, potentially significantly reduce risk for patients with abdominal emergencies.

### 5. PRELIMINARY STUDIES AND EXPERIENCE OF INVESTIGATORS

This study is a continuation of a long-standing collaboration between the University of Portsmouth (UoP) and Portsmouth Hospitals NHS Trust (PHU). The team has 20 years of experience in extracting and linking these types of data sets for work in clinical outcome modelling and risk prediction.

Our work has previously led to the development of VitalPAC, P-POSSUM (Portsmouth Physiological and Operative Severity Score for the enUmeration of Mortality and morbidity) (18) and ViEWS. NEWS was a minor modification of ViEWS and its latest version (NEWS2) is now mandated for use in NHS hospitals and ambulance trusts (37,22). P-POSSUM, although initially developed as an audit tool, was recommended for use by the Royal College of Surgeons in 2011 as pre-operative risk prediction tool (2). They quote:- "P-POSSUM, freely available on the internet, is possibly the simplest and best-validated method" and: "The POSSUM score is the most validated risk prediction method for general and vascular patients that takes into account pre-operative and peri-operative factors. P-POSSUM may be used for all patients. A predicted mortality risk  $\geq 10\%$  indicates a need for critical care admission, except for patients on end-of-life pathways with appropriate palliative care facilities available at ward level."

Importantly, this team has a track record and ongoing studies of the outcomes of major abdominal surgery and less-invasive approaches, as evidenced by these 2 recent publications in peer reviewed journal:

## **6. AIMS AND OBJECTIVES**

### **6.1 Aim**

The overall aim of this study is to improve the quality of care for patients with an abdominal emergency, irrespective of whether they have a laparotomy or not. The evidence gathered will provide new estimates of the average risk of death for different treatment options and inform the development of care pathways. In addition to guiding clinical decisions, our findings will make more robust the communication with patients and relatives around different treatment options.

### **6.2 Objectives**

1. Identify all patients with a condition that would qualify them for emergency abdominal surgery, both laparotomy and keyhole (laparoscopic) procedures, regardless of whether they had surgery

or not. This will be done by filtering electronic hospital records for appropriate diagnosis and operation codes.

2. Provide updated estimates of the average risk of death for different treatment options, including surgical and non-surgical intervention, using statistical analysis of short-term and long-term outcomes. Describe health characteristics of the typical patient population receiving one of the treatment options, based on their clinical data and an established risk index.
3. Logistic regression will be used to predict the risk of death for each patient group and each treatment option, which will allow identification of the best care pathways given a patient's health characteristics.
4. Identify patients who would have likely benefited from a different care pathway than the one they received, using machine learning classification algorithms

Our analysis will form the foundation for the establishment of four well-defined care pathway options, each with the patient's best interest in mind: laparotomy, laparoscopy, other alternative treatment, and end of life care.

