## 7. STUDY DESIGN

### 7.1 Summary of Study Design

This single-centre retrospective cohort study will use data derived from electronic patient records collected as part of routine patient care. It will be conducted at Portsmouth Hospitals University Trust NHS Trust, a large acute District General Hospital. Logistic regression and other classical statistical techniques will be used to predict the risk of death for different treatment methods and to identify clusters of patients with the same characteristics. This will allow identification of lower-risk treatment options for different patient groups.

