### 10.2 Data analysis

Extracted data will be cleaned and quality controlled prior to analysis to ensure all relevant patients have been extracted. Given that our analysis will use only routinely collected, clinical data, missing values are unlikely to pose an issue. Initial analysis of 2018 data confirmed that clinical data within 24h of admission was almost fully complete for a remarkable >97% of admissions, meaning there is likely no need to impute data. We will test whether excluding admissions with missing data will introduce bias.

Our analysis can be broken down into the following steps:

- Comparison of the four treatment groups based on demographics, outcomes and medical pathway. This will include calculating mortality and long-term complication rates (Objective 2).
- Construct and compare risk models for each treatment group to predict short-term and long-term risk and to investigate the effect of both patient and hospital-level factors on outcome (Objective 3).

- Identify patients in each group who are abnormal for the group and might have fared better with a different treatment, using clustering algorithms (Objective 4).

After splitting the data set into subsets for each of the four patient groups using diagnosis and procedure codes (see above), mortality and long-term complication rates will be calculated for each group. Longer-term follow-up will include rates of re-admission to hospital, additional theatre visits and development of new medical conditions, within one year of initial admission with an abdominal emergency. Results will provide updated estimates of the average risks of different surgical procedures as well as the risk of not having surgery. Results will be compared with P-POSSUM mortality. Patient groups will further be characterised the using patient factors. Parameters of interest will include but are not limited to age, sex, mortality, long-term complication rates, admission early warning scores (NEWS, LDTEWS and LDTEWS:NEWS), frailty, medical history (previous ICD-10 codes).

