Patient group characteristics will be summarised with proportions for nominal and ordinal variables, means and standard deviations for continuous variables having symmetric unimodal distributions, and medians and interquartile ranges for other continuous variables. Clinical outcomes will be reported as proportions with 95% confidence intervals. Statistical tests of differences in proportions (Chi - nominal variables) and means/medians (ANOVA/Kruskal-Wallis) will be performed. Post-hoc pairwise comparisons will be carried out using Scheffe's method for ANOVA and Dunn's test for Kruskal-Wallis results and Bonferroni corrections for Chi results with significance at  $p < 0.05$ .

In the next step, we will identify which patient characteristics affect the outcome for a specific care pathway. Candidate predictor variables of 30-day mortality will be assessed with simple univariable linear regression and check for non-linearity. For each treatment group, we will construct a logistic regression model with the candidate predictor variables and non-linear terms as needed. Logistic regression performance will be tested using "goodness of fit" and discrimination. Goodness of fit, the ability to correctly predict risk, will be evaluated using the Hosmer-Lemeshow statistic (28) and by 10-fold cross-validation. Discrimination, the ability to rank cases in terms of risk, will be assessed using the Area Under the Receiver Operating Characteristic Curve (AUROC) (29). The relative importance of individual parameters will be assessed by the parameters Wald and t-statistics.

The last objective is to determine outlier clusters of patients who might have fared better on a different care pathway. For each treatment group, machine learning classification algorithms will be used to identify homogenous clusters of admissions in terms of their attributes. Each clustering will be reported by its method, number of clusters and intracluster correlation coefficients (ICCs) with 95% confidence intervals and used to extend the logistic regression risk model for the treatment group to see if the model is improved as measured by a likelihood ratio test. Where this is the case the patient subgroups corresponding to the clusters will be analysed in terms of their clinical characteristics.

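### Objective 3 infers the best pathway from models fitted separately in patients selected for each treatment, with no overlap check or assessment of residual confounding by indication

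*Protocol*

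**What the plan says.** Objective 3 (Protocol 6.2) predicts risk of death for each patient group and treatment option, "which will allow identification of the best care pathways given a patient's health characteristics". Section 7.1 draws the same inference: "This will allow identification of lower-risk treatment options for different patient groups". Section 7.3 repeats it almost word for word.

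The method is in section 10.2. The analysis steps include: "Construct and compare risk models for each treatment group to predict short-term and long-term risk". The model structure is fixed: "For each treatment group, we will construct a logistic regression model with the candidate predictor variables and non-linear terms as needed". Goodness of fit "will be evaluated using the Hosmer-Lemeshow statistic (28) and by 10-fold cross-validation", and discrimination is assessed by AUROC.

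Section 10.1 lists the recorded patient factors: age, demographics, diagnosis, co-morbidities, frailty, vital signs and blood tests.

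Section 4.3 describes how treatment was chosen in the cited cohort of 314 patients. Of those not operated on, "74% were not felt to be fit enough for laparotomy". They were also older (78 versus 63.7 years) and are described as frailer. On their mortality exceeding the risk-model predictions, the Protocol says: "The discrepancy could be due to unmeasured confounding patient factors that are not included in the risk model".

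**The concern.** Calling one option lower risk for a given patient is a statement about what would happen to that patient under a different treatment. A model fitted only to operated patients describes people judged fit for an operation. Applied to someone judged unfit, it assumes that the recorded covariates explain the whole difference between the two kinds of patient, and that enough similar patients were operated on to support the prediction. The Protocol neither states nor checks either condition, although it recognises the problem in the study that motivates this one.

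The planned checks cannot show a failure. Hosmer-Lemeshow, cross-validation and AUROC all ask whether a model predicts well within its own group. A logistic model with an intercept reproduces its own group's death rate by construction, however that group was selected.

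Sections 6.1 and 15.1 intend the results to guide clinical decisions, care pathways and patient information, so a difference created by selection could be passed on as a treatment effect.

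**Working it through.** **1. The Protocol's own figures (section 8).** In 2018 there were 901 patients, 530 with surgery and 901 − 530 = 371 without.
- Scaling: 901 × 6.5 = 5,856.5 (stated: over 5,800); 530 × 6.5 = 3,445 (stated: over 3,400).
- In-hospital deaths: 23/530 = 4.34% (stated 4.3%); 28/371 = 7.55% (stated 7.6%).

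All are reproduced. The Protocol gives no effect size for a between-treatment comparison.

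**2. Crude contrast, no surgery versus surgery.**
- RR = (28/371)/(23/530) = 1.74; risk difference 3.2 points.
- SE(log RR) = √(1/28 − 1/371 + 1/23 − 1/530) = 0.273.
- 95% CI = exp(0.553 ± 1.96 × 0.273) = 1.02 to 2.97.

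**3. E-value = RR + √(RR(RR − 1)).**
- Estimate: 1.739 + √(1.739 × 0.739) = 2.87.
- Lower limit: 1.018 + √(1.018 × 0.018) ≈ 1.15.

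A factor associated by a risk ratio of about 2.9 with both non-operation and death could account for the whole crude ratio. About 1.15 would move the lower limit to 1.

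**4. The planned comparison when treatment has no effect.** The simulation has a measured score X and an unmeasured unfitness factor U, both standard normal:
- logit P(surgery) = c − 0.5X − aU
- logit P(death) = b + 0.7X + aU, with no treatment term

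Here c gives 58.8% surgery and b gives (23 + 28)/901 = 5.66% deaths. A logistic model on X is fitted in each group, and both models then predict for every patient. There are 5,856 patients and 400 replicates. The slopes and a are assumptions; the documents give none.

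| a | Crude death rate, surgery / none | Mean predicted, surgery / none | False benefit | Patients assigned lower risk with surgery |
|---|---|---|---|---|
| 0 | 4.9% / 6.7% | 5.66% / 5.66% | 0 points | 48% |
| 0.5 | 4.5% / 7.4% | 5.06% / 6.32% | 1.3 points | 92% |
| 0.7 | 4.1% / 7.9% | 4.61% / 6.85% | 2.2 points | 98% |

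The false difference exceeds 1.96 empirical standard deviations in 50% of replicates at a = 0.5 and 93% at a = 0.7. With 1,000,000 patients, a = 0.3 gives 0.5 points and a = 1.0 gives 4.0 points. The crude rates at a = 0.7 are close to the Protocol's 4.3% and 7.6%.

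**5. Overlap, with selection on a measured factor only.** There is again no treatment effect, but the true risk curve is bent and the fitted model is linear. For patients with a score above 1.5 SD the true risk is 22.4%.

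| Selection slope on the score | Surgery model predicts | No-surgery model predicts |
|---|---|---|
| 0.5 | 13.7% | 19.5% |
| 1.5 | 8.4% | 20.9% |
| 3 | 5.3% | 21.5% |

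As overlap worsens, the surgery model extrapolates further below the truth.

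**6. How much depends on what is recorded.** A second null simulation (5,857 patients, 60 replicates) used a binary unfitness factor with odds ratio 4 for death and 5 against surgery. The share of patients for whom surgery is called lower risk depends on how well a recorded frailty variable captures that factor:
- not recorded: 99%
- sensitivity 0.70, specificity 0.90: 90%
- sensitivity 0.90, specificity 0.95: 77%
- fully captured: 50%, as expected by chance

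**The case against.** The strongest reply is that the plan does adjust. Age, diagnosis, co-morbidity, frailty, vital signs, blood tests and prior history are candidate predictors, with non-linear terms allowed. Comparing outcome models fitted by treatment arm, given such covariates, is a recognised form of standardisation. This stands: a reader might infer that selection is not controlled at all, and section 10 does not support that. The gap is the absence of any check on whether this adjustment suffices.

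A reader might also infer that nearly every patient would wrongly be told surgery is safer. The 99% figure assumes unfitness is entirely unrecorded, and it counts any difference, however small. The documents do not say how well frailty will be captured. The average false gap in points is the better measure.

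Nor do the 2018 data show that surgery has no effect. They are compatible with none, but the interval is wide. They concern in-hospital death, whereas section 10.2 assesses predictors of 30-day mortality. The two-group calculations also say nothing about laparoscopy versus laparotomy.

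Weighting on the same covariates is not a cure. In the simulation with odds ratios 4 and 5 and unfitness unrecorded, overlap weighting left a false benefit of 2.7 points, against 2.6 from separate models. A propensity limit of 0.1 to 0.9 would have excluded nobody.

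Finally, weighting and sensitivity analyses are often left to a statistical analysis plan, and section 15.3 calls this study a first step. But the Protocol itself fixes both the separate-model method and the conclusion to be drawn from it, and section 15.1 carries the findings into care pathways and patient information.

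**Conclusion.** The concern holds in a limited form. Followed as written, Objective 3 can turn treatment selection into an apparent treatment benefit, and none of the planned checks would reveal it. The crude ratio of 1.74 could arise from moderate residual selection alone. Under the assumed strengths the false benefit of surgery is roughly 1 to 3 percentage points (0.5 to 4.0 across the wider range tried). It is zero if the recorded covariates capture all selection, overlap is adequate and the models are correctly specified. Overlap is likely to be weakest for the end-of-life group, which is defined by treatment being futile. The direction and mechanism do not depend on the exact assumptions; the sizes do. This should be settled before Objective 3 is run.

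**What to change.** In section 10.2:
- Use one common set of pre-treatment covariates for every between-treatment contrast, drawn from the variables in section 10.1.
- Check covariate or propensity overlap, report the share of each group outside common support, and make no between-treatment comparison for those patients.
- Add an E-value or quantitative bias analysis for unmeasured fitness.

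Whether the contrast is then estimated by outcome modelling or by weighting is a trade-off for the team.

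In sections 6.2, 7.1 and 7.3, replace the best-pathway and lower-risk-option wording with predicted risk under the treatment received, unless the adjusted contrast and the bias analysis support more.

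The cost is some extra analysis on data already planned for extraction, fewer patients per contrast and wider intervals.
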